**Schema**

This 40-patient pilot, double-blinded, placebo-controlled trial entails the administration of lipids versus placebo x 1 dose before every dose of carboplatin or oxaliplatin. The primary endpoint will be time-to-carboplatin or oxaliplatin hypersensitivity reaction, and exploratory laboratory endpoints will be examined during the first cycle of carboplatin or oxaliplatin.

Max cycle length = 28 days (will vary by agent please see Section 7.0 for details)  
Max study duration per patient = 2 years after registration

Generic name: lipid emulsion Brand name: Intralipid® 20% Mayo Abbreviation: NA Availability: Provided for study	Generic name: placebo Mayo Abbreviation: NA Availability: Provided for study
--	--

## 1.0 Background

### **1.1 The Important Role of Carboplatin and Oxaliplatin in Cancer Treatment**

Carboplatin is a key antineoplastic agent for the treatment of ovarian cancer. Over the past decade, it has served as the backbone chemotherapy agent for the majority of postoperative ovarian cancer trials. Indeed, the well-established term “platinum sensitive disease” refers to the 6-month cancer-free interval after which it becomes acceptable to re-expose patients to this drug upon cancer recurrence, thus further underscoring the pivotal role of carboplatin for the treatment of this malignancy [1-5]. Carboplatin has also become a key drug in the treatment of other gynecological malignancies, such as endometrial cancer.

The same can be said for oxaliplatin, which is used extensively in the treatment of patients with gastrointestinal cancers. One might argue there are few/no gastrointestinal cancers that cannot be treated with an oxaliplatin-based regimen. Oxaliplatin is a key drug as adjuvant chemotherapy in colorectal cancer patients [see extra references].

### **1.2 Carboplatin and Oxaliplatin Hypersensitivity Reactions: Incidence, Risk Factors, and Management**

Carboplatin and oxaliplatin hypersensitivity reactions can interfere with cancer treatment and compromise such ongoing cancer therapy. These reactions are **life-threatening and obvious** when they occur. They are characterized by itching, coryzal symptoms, nausea and vomiting, dyspnea, wheezing, hypotension, confusion, and, at times, even death. For carboplatin, reactions occur in only 10% of patients during the first 6 cycles of chemotherapy, but their incidence jumps to approximately 30% shortly after the 7th cycle of carboplatin [6]. For oxaliplatin, the incidence appears to increase with the 7th cycle of treatment as well to a rate of approximately 20% with a steady increase in incidence thereafter [see extra references].

Risk factors for these reactions include a predisposition to allergies, a higher cumulative dose of the culpable drug, and specific choice of concurrently administered chemotherapy agent [6-14]. One of the most powerful risk factors is time-dependent: patients with a 13 month or longer carboplatin-free interval have a **22-fold increased risk** of a reaction upon re-exposure [8]. Although earlier studies had invoked skin testing to identify patients at risk, most medical centers do not make use of this approach because of suboptimal predictive sensitivity and specificity, mutilating cutaneous effects, and undue chemotherapy exposure for healthcare workers and the environment [15]. Vigilance during drug infusion and either desensitization or abandonment of either carboplatin or oxaliplatin post-reaction comprise the current approach to platinum drug administration.

Desensitization enables carboplatin or oxaliplatin to be dispensed once again with small, incremental doses administered in a monitored setting until the entire intended dose is infused [16-21]. Desensitization has drawbacks: **1) a several-hour commitment with every infusion; 2) reduced but ongoing risks of hypersensitivity signs/symptoms with mounting risk over time; and 3) exorbitant cost.** At our institution, over one year, we observed cumulative, multi-cycle patient costs with desensitization to carboplatin specifically of **\$1 million – over a 10-fold increase** over that incurred from routine outpatient carboplatin administration. An inexpensive prophylactic intervention that **eliminates carboplatin and oxaliplatin reactions** would be advantageous for many reasons.

### 1.3 Addressing a Gap

Few studies have examined a **prophylactic approach** to these reactions. A commonly-used intervention to prevent reactions, as proposed here, provides a safe, potentially cost-effective, and novel way of managing the risk for a carboplatin hypersensitivity reaction.

Table 1: RANDOMIZED TRIALS WITH DOXIL® + CARBOPLATIN VERSUS CARBOPLATIN WITH NO DOXIL®			
TRIAL	N	REACTION RATE with DOXIL® (%)	REACTION RATE with CARBOPLATIN with NO Doxil® (%)
Markman, 2010 [22]*	61	0	30
Bafaloukos, 2010 [23]*	189	8	30
Pujade-Lauraine, 2010 [24]	976	15	33

\*Not specified whether Doxil® was infused first.

### 1.4 Hypothesis: Lipids Prevent Carboplatin Hypersensitivity Reactions

This proposal focuses on a **seminal, recurrent observation**: relapsed cancer patients who receive liposomal doxorubicin (Doxil®) with carboplatin **suffer fewer carboplatin reactions (Table 1)**. Of note, in Table 1, some of the reactions with Doxil® might perhaps have been attributable to Doxil®, which at times can also cause hypersensitivity reactions – and perhaps **not at all to carboplatin**. Nonetheless, throughout the published literature, the rate of carboplatin hypersensitivity reactions is consistently <30% with the incorporation of Doxil®, even in single-arm trials [22-30]. The seminal observation that Doxil®, a liposomal form of doxorubicin, is associated with lower rates of carboplatin hypersensitivity reactions gives rise to the following novel **HYPOTHESIS: the infusion of a lipid emulsion (the same used for nutrition support) – in effect, liposomal doxorubicin but without the doxorubicin – prevents carboplatin hypersensitivity reactions.**

Three points underscore the plausibility of this hypothesis. **First**, again, Doxil® is associated with fewer carboplatin hypersensitivity reactions [22-30]. Lipid emulsions, as commonly prescribed for parenteral nutrition, simulate Doxil® infusions by providing a near identical therapeutic platform -- same volume, similar lipids – but with **no Doxil®**. **Second**, carboplatin hypersensitivity reactions are most commonly type I hypersensitivity reactions (and less commonly type IV hypersensitivity), as indicated by a series of studies that demonstrate IgE mediation [10,11,31,32]. Lipid emulsions, particularly those that are heavily soy-based and commonly prescribed today, have immunosuppressive effects [33-35]. They transiently suppress T-cell function, modulate B cell populations, and confer other suppressive effects on inflammation [33-35]. Of special relevance, preclinically, Arnaez and others, showed that, although carboplatin induces histamine release from mast cells, it does so by **unique mechanisms – speculatively, via complement activation or direct mast cell degranulation – but nonetheless unrelated to conventional approaches** [36]. These findings are in keeping with what occurs clinically where carboplatin reactions remain problematic and suggest that a **broad-based immunomodulator, such as a lipid emulsion**, merits testing, as proposed here.

**Third, and very importantly**, multiple reports indicate that **lipid emulsions (the same used for nutrition support) are critically life-saving in patients with severe drug-induced adverse events** [37-47]. These reports describe the resuscitative role of lipids -- often as a heroic last resort -- in patients with overdoses from mepivacaine, bupivacaine, olanzapine, doxepin, flecainide, venlafaxine, moxidectin, atenolol, nebivolol,

lamotrigine, propranolol, verapamil, diltiazem, atenolol, amitriptyline, glyphosate herbicide, and others [37-47]. In effect, lipids serve as a rescue for patients suffering from toxicity from a lipophilic drug: in some reports, patients who were suffering ventricular tachycardia and who were seizing recovered promptly upon receipt of a lipid infusion. It appears that the infused lipids bind to the lipophilic drug and displace it from the target organ. In the case of **carboplatin and oxaliplatin – both of which are highly lipophilic – lipids presumably bind to it, displace it from basophils and mast cells, and thereby prevent the hypersensitivity reaction.**

Lipid emulsions are used as part of parenteral nutrition to increase the caloric content of nutrition support and to prevent essential fatty acid deficiency. Various lipid emulsions are available, are commonly prescribed, and have been used for decades. Individual patients with bowel failure have been maintained on nutrition support for many, many years with weekly lipid infusions. These lipid emulsions tend to be well tolerated with adverse events noted in section 15.0.

### **1.5 Special Safety Considerations**

We do not know whether lipids would influence the efficacy of chemotherapy. Two points suggest that lipids would not do so. First, prior studies with Doxil® and carboplatin show that these drugs together have favorable antineoplastic activity; analogously, a lipid emulsion **would not appear to detract** from the antineoplastic effects of either of these platinum-based agents [22-30]. Second, parenteral nutrition that includes concomitant lipid administration to increase caloric content is used often in various cancer settings, such as in patients undergoing bone marrow transplantation and in perioperative patients with severe malnutrition.

However, in an effort to be extra cautious in the current study, we will monitor patients closely during the trial, and we will also exclude patients who are being treated with curative intent.

### **1.6 Pathobiology.**

[figure not shown]
Because of the life-threatening nature of carboplatin and oxaliplatin reactions, pragmatic considerations have resulted in sparse studies on pathobiology. These studies indicate these reactions are commonly type I and less commonly type IV [31,48]. First, emphasizing their type I nature, Iwamoto and others observed CD203c, a basophil surface marker of IgE-mediated type I hypersensitivity reactions, was 15% higher in patients who had sustained a carboplatin-induced reaction compared to those who had not [48]. Second, Caiado and others reported that 59% of patients who had sustained a carboplatin reaction had a carboplatin-specific IgE [32]. Third, Hesterberg and others demonstrated serum tryptase elevation in patients with a carboplatin hypersensitivity reaction [10]. **Serum tryptase, the most abundant mediator of hypersensitivity reactions stored in mast cells**, is one of 4 key mediators that comprise a standard panel of diagnostic evidence of allergic reactions: 1) serum tryptase, 2) urine 11-beta prostaglandin F2 alpha (PGF2a), 4) urine leukotriene 4, and 5) urine N-methylhistamine, the latter three of which stem from the release of prostaglandins, leukotrienes, and histamine, respectively. This finding of tryptase elevation with carboplatin or oxaliplatin reactions further emphasizes that these are type I hypersensitivity reactions and suggests a role for this 4-mediator panel [48-52]. Fourth, workers exposed to platinum salts show reactions to metals are mast cell/basophil IgE-mediated [53-55]. Finally, and of special relevance, preclinical work indicates that, although carboplatin induces histamine release from mast cells, this agent does so by **unique, inexplicable mechanisms unresponsive**

to more conventional suppressive agents; therefore, **novel interventions** are needed to prevent these reactions [48]. These findings indicate that IgE-mediation plays a complex but not fully elucidated role in carboplatin and oxaliplatin hypersensitivity reactions. Thus, it is reasonable to use a standard panel of 4 mediators -- serum tryptase; urine 11-beta prostaglandin F2 alpha (PGF2a); urine leukotriene E4; and urine N-methylhistamine, the latter 3 of which have not been assessed in carboplatin or oxaliplatin reactions but logically stem from release of prostaglandins, leukotrienes, and histamine, respectively -- to understand pathobiology and its relevance [56].

**Figure 1:** The median survival of ovarian patients who had a carboplatin reaction and who underwent desensitization was 1.4 years (95% confidence intervals: 1.07, 1.96 years). These data show that desensitization procedures are associated with long survival. These data suggest that the continued use of carboplatin and the investigation of approaches to reduce the risk of hypersensitivity reactions are justified.

slowed. This observation **illustrates the need to prevent carboplatin reactions in the first place and the need to find ways to circumvent desensitization procedures.**

### 1.8 Summary

In view of the fact that reactions to carboplatin and oxaliplatin can compromise cancer care and can augment cost related to cancer care, we propose to test a simple, rationale, cost-effective prophylactic intervention, namely, the administration of lipids prior to patients' receiving their 7th or later infusion of either carboplatin or oxaliplatin. This proposal aims to test the hypothesis that lipids decrease the incidence of hypersensitivity reactions to these drugs within the context of a placebo-controlled trial.

[figure not shown]
### 1.9 Correlative Studies: Blood and Urine Markers

**Although exploratory in nature, this aim would potentially afford the scientific underpinnings for a large scale clinical trial to be conducted in the Alliance for Clinical Trials in Oncology. This aim therefore plays an essential role in this pilot project.** Laboratory endpoints will be checked only with the first dose of carboplatin following trial enrollment at three time points: within 24 hours prior to the lipid/placebo infusion (#1); after the lipids/placebo infusion (#2); and after the carboplatin/oxaliplatin infusion (#3) (**Figure 3**). Time point #2 will include only a blood check because of time constraints. Time points #1 and #2 are scientifically justified because all patients **will have received carboplatin/oxaliplatin earlier and are therefore potentially immunologically “primed”** to react to it. From a practical standpoint, it is **unlikely** that a patient who has sustained the trauma of a reaction would be willing to have her blood/urine checked at time point #3; nonetheless, time points #1 and #2 enable us to learn whether lipids appear to modulate well-established mediators of hypersensitivity reactions and whether these established mediators/ biomarkers are able to predict reactions.

[figure not shown]
We anticipate reporting data only descriptively (no sample size calculations) because of a high likelihood of patient drop-out at time point #3.

Again, the purpose of this exploratory translational aim is to acquire **preliminary evidence of the immunomodulatory effects of lipids on mediators of hypersensitivity reactions.**

**Assays.** We will focus on four mediators, all with inter- and intra-test coefficients of variation of <15% (**Figure 4**). Blood and urine will be obtained, per the three time points in **Figure 3** where carboplatin refers to either carboplatin or oxaliplatin, with the first cycle of carboplatin following enrollment. We choose to focus on only the **first cycle** because 1) this allows us to accomplish our goal of acquiring evidence of the immunomodulatory effects of lipids

**Figure 3:** Translational endpoints will be assessed per the schema above at time points #1, #2, and #3.

**Figure 4:** Four well-established mediators of hypersensitivity reactions -- serum tryptase, urine 11-beta prostaglandin F2 alpha (PGF2a), urine leukotriene 4, and urine N-methylhistamine -- will be used as markers provide further clinical evidence of reduced hypersensitivity reactions with lipids adapted from Bax, et al, 2012).

as relevant to hypersensitivity reactions; 2) more frequent testing poses an undue patient burden; and 3) cost is otherwise prohibitive in this pilot trial setting.

## 2.0 Goals

- 2.1 To determine if the infusion of a lipid emulsion before each dose of chemotherapy appears to prevent carboplatin and oxaliplatin hypersensitivity reactions in high-risk patients.
- 2.2 To explore if lipid infusions modulate a well-established panel of mediators of hypersensitivity reactions and if these mediators appear to predict reactions.

## 3.0 Patient Eligibility

- 3.1 Inclusion criteria
  - 3.11 Age  $\geq$ 18 years
  - 3.12 Advanced, incurable cancer
  - 3.13 7th or later cycle of intravenous carboplatin or oxaliplatin infusion planned or 4 months after the first cycle of agent (whichever is of longer duration)  $\leq$ 30 days after registration
  - 3.14 Anticipated 2 or more subsequent chemotherapy infusions of either carboplatin or oxaliplatin at the time of study registration.  
NOTE: The dose of carboplatin or oxaliplatin, choice of other chemotherapy, and other ancillary treatment, such as antiemetics, will be left to the discretion of the treating healthcare provider.
  - 3.15 Willing to provide mandatory blood and urine specimens for correlative research.  
Note: Can be waived with permission of Study Chair (documentation such as an email must be provided).
  - 3.16 The following laboratory values obtained  $\leq$ 30 days prior to registration:
    - Serum creatinine  $\leq$ 1.5 times the institutional upper limit of normal (ULN)  
Note: Can be waived with permission of Study Chair (documentation such as an email must be provided).
    - Aspartate aminotransferase (AST) or Alanine aminotransferase (ALT)  $<3$ x the upper limit of normal.
    - Triglycerides  $<500$  mg/dL
    - Alkaline phosphatase  $\leq$ 3x the institutional upper limit of normal.
- 3.2 Exclusion Criteria
  - 3.21 Concurrent liposomal doxorubicin or any other liposomal agent.
  - 3.22 Prior carboplatin or oxaliplatin hypersensitivity reaction.
  - 3.23 Taking aspirin, nonsteroidal anti-inflammatory agents, or zileuton  $\leq$ 7 days prior to registration.  
Note: Can be waived with permission of Study Chair (documentation such as an email must be provided).
  - 3.24 Allergy to egg or egg byproducts.

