## 9.0 Ancillary Treatment/Supportive Care

### 9.1 Full supportive care

Patients should otherwise receive full and appropriate supportive care as clinically indicated.

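### Criterion 3.21 excludes liposomal drugs but not non-study intravenous lipid emulsion, so a patient receiving the study agent as nutrition can be randomised to placebo (minor; cheap to close)

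*Combined protocol and SAP*

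**What the plan says.** Section 3.2 has four exclusions. The one concerned with lipid carriers, 3.21, reads "Concurrent liposomal doxorubicin or any other liposomal agent". The others cover a prior platinum reaction, certain anti-inflammatory drugs and egg allergy. None names intravenous lipid emulsion or parenteral nutrition.

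Section 1.4 ties the study agent to nutritional lipid. Its hypothesis concerns "the infusion of a lipid emulsion (the same used for nutrition support", and it adds that "Lipid emulsions, as commonly prescribed for parenteral nutrition, simulate Doxil® infusions by providing a near identical therapeutic platform". It also notes that "Individual patients with bowel failure have been maintained on nutrition support for many, many years with weekly lipid infusions". Section 1.5 says that "parenteral nutrition that includes concomitant lipid administration to increase caloric content is used often in various cancer settings", and gives bone marrow transplantation and malnourished perioperative patients as examples.

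Concomitant care is open. The note under 3.14 says that "other ancillary treatment, such as antiemetics, will be left to the discretion of the treating healthcare provider", and 9.1 says "Patients should otherwise receive full and appropriate supportive care as clinically indicated". Sections 7.1 (treatment) and 13.4 (off-study reasons) do not restrict non-study lipid. The calendar in 4.1 and the descriptive factors in 12.0 do not list it.

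**The concern.** The trial compares lipid with no lipid. Criterion 3.21 keeps out a drug that the protocol treats as an analogue of the study agent, yet lets in the agent itself when it is given for another purpose. A placebo patient who receives nutritional lipid around the time of platinum is not a clean control.

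Two things are at stake. For goal 2.1, if lipid works, exposed placebo patients react later than they otherwise would, and the arms look more alike. For goal 2.2, time point #1 is meant as the sample before lipid (section 1.9), and in such a patient it might not be. The doubling of the sample size from 20 to 40 in 16.4 is justified by censoring alone, so it makes no explicit allowance for this.

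**Working it through.** **1. Does any other text close the gap?** Criteria 3.11 to 3.24 and sections 7.1, 9.1 and 13.4 contain no bar on non-study lipid. The nearest limit is the triglyceride ceiling of 500 mg/dL in 3.16. It applies once, before registration, and does not exclude a nutrition recipient whose value is below it. The gap is real.

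**2. The plan's own figure.** Inputs from 16.4: hazard ratio 3.8, one-sided 5% level (z = 1.645), 80% power (z = 0.842), 1:1 allocation, 20 patients before inflation.
- Freedman: (1.645 + 0.842)² × (4.8/2.8)² = 18.2, so 19 events. This is consistent with the stated 20 patients if nearly all react.
- Schoenfeld: 4 × (1.645 + 0.842)² / (ln 3.8)² = 13.9, so 14 events.

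The plan states no event target. The stated size is reproduced most closely by Freedman's formula.

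**3. Expected events at the enrolled size.** Inputs: 20 per arm (16.4), 4 months on treatment (16.5), median about 2 months (16.4; the arm is not named and is taken here as placebo), exponential times. The lipid-arm median is then 2 × 3.8 = 7.6 months.
- Placebo: 1 − 2^(−4/2) = 0.75, so 15.0 events.
- Lipid: 1 − 2^(−4/7.6) = 0.306, so 6.1 events.
- Total: about 21 events.

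**4. Effect of exposed placebo patients.** Let a fraction c of placebo patients have the full lipid-arm hazard. The documents do not give c, so the range is an assumption. The initial hazard ratio is 3.8 × [(1 − c) + c/3.8]. For c = 5% this is 3.61 + 0.05 = 3.66; for 10%, 3.42 + 0.10 = 3.52; for 20%, 3.04 + 0.20 = 3.24.

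Power comes from a simulated one-sided log-rank test. Where a range is shown, separate runs differ by about a point.

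| Exposed placebo patients | Power, 20 per arm, 4 months | Power, 10 per arm, every patient reacts |
|---|---|---|
| 0% | 91-92% | 86-87% |
| 5% (1 of 20) | 88-89% | 79% |
| 10% (2 of 20) | 85% | 72% |
| 20% (4 of 20) | 76-77% | 59% |

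The middle column uses the enrolled size but no censoring before 4 months. The right-hand column uses the plan's base size of 10 evaluable patients per arm.

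**5. How far full effect can be assumed.** Study lipid is given immediately before platinum (7.1), and its elimination half-life is 0.5 to 1 hour (15.15). Two hours after an infusion ends, 2 to 4 half-lives have passed and 25% to 6% remains. After five hours, 5 to 10 half-lives have passed and 3% to 0.1% remains. Lipid running on the chemotherapy day could overlap with platinum; lipid given on other days would be largely cleared. The losses in step 4 are therefore upper bounds. The lower bound is no loss.

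**The case against.** The strongest case against is that the gap may have no practical effect.

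- **Frequency.** The examples in 1.5 are transplant and perioperative patients. Trial patients have incurable cancer, are at a seventh or later platinum cycle and are expected to have at least two more infusions. The bowel-failure remark in 1.4 does not say those patients have cancer. With 20 per arm, no exposed placebo patient at all is plausible. This stands.
- **Pharmacology.** The short half-life limits any effect of lipid given at other times. This stands as a limit on size. It does not remove the concern, because 1.4 also proposes transient immune suppression, whose duration is not given, and two of the three trials in Table 1 did not specify whether the liposomal drug was infused first.
- **Purpose of 3.21.** The protocol does not give the reason for this criterion. Section 1.4 notes that liposomal doxorubicin can itself cause hypersensitivity reactions, and that reason would not extend to nutritional lipid. So 3.21 cannot be called inconsistent with its own stated purpose.
- **Direction.** If lipid has no effect, exposed controls change nothing, so this cannot create a false positive.

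Some stronger readings are tempting. A reader might infer that patients on home nutrition are typical candidates, or that they would receive more lipid than the lipid arm; the documents support neither. A reader might also infer that such lipid goes unrecorded. The case report forms and the Data Submission Schedule are not among the documents, so absence from 4.1 and 12.0 does not show that. The effect on goal 2.2 should not be pressed far either, since the mediator data are descriptive and hypothesis-generating (1.9, 16.32).

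**Conclusion.** The gap in 3.21 is real, and no other section in the documents closes it: a patient receiving non-study lipid emulsion is eligible and can be assigned to placebo. Any bias in goal 2.1 would be towards no effect, and a time point #1 sample could be exposed to lipid before the study infusion.

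The consequence is minor. At the enrolled size and on the plan's own assumptions, even full lipid effect in 10% of placebo patients leaves power at about 85%; it falls below 80% only in the 20% case. At 10 per arm the loss is steeper, and 5% is enough to bring power to about 79%. Heavy early censoring, which 16.4 expects, would move the trial towards that less favourable case. All of these figures rest on an assumed frequency and on worst-case effect, and the true loss may be nil. They do not show that the trial is underpowered for this reason, or that a null result would be uninterpretable.

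**What to change.** Extend 3.21 by adding, after the liposomal agents already named, *or non-study intravenous lipid emulsion (including lipid-containing parenteral nutrition)*.

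An entry criterion cannot deal with lipid started later. For that, make sure the case report forms record with dates any non-study intravenous lipid given on study; if they already do, nothing need be added. Keep such patients in the primary analysis as randomised. Use the record only for a secondary sensitivity analysis, for example censoring at the first such lipid, and state that this censoring may be informative because starting nutrition can mark deterioration. Whether nutrition is given remains with the treating team.

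The cost is one phrase in the protocol, at most one form item, and one optional analysis. The downside is the loss of the few candidates already receiving parenteral lipid. The planned sample size does not change.

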#### 4.0 Test Schedule

##### 4.1 Study Calendar

Tests and procedures	≤30 days prior to registration	With the first on-study infusion of carboplatin or oxaliplatin	Immediately before each infusion of carboplatin or oxaliplatin	End of each cycle of carboplatin or oxaliplatin
History and exam including weight	X			X 
Serum creatinine	X			
AST or ALT	X*			
Triglycerides	X			
Alkaline phosphatase	X*			
Lipid/placebo infusion			X	
AE Assessment	X			X
Blood and urine collection for research purposes R		X		

\*Should be retested every 3 months or per the discretion of the treating oncologist.

Maximum Cycle Length = 28 days (will vary by regimen)

Footnotes:

1. Weight only

R Research funded

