### 6.5 Start of treatment

Treatment cannot begin prior to registration and must begin  $\leq 14$  days after registration.

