## 14.0 Body Fluid Biospecimens

### 14.1 Summary Table of Research Blood and Body Fluid Specimens to be Collected for this Protocol\*

Correlative Study (Section for more information)	Mandatory or Optional	Blood or Body Fluid being Collected	Type of Collection Tube (color of tube top)	Volume to collect per tube (# of tubes to be collected)	24 hours prior to lipid/placebo infusion	Within 2 hours following lipid infusion	24 hours after chemo infusion	Process at site? (Yes or No)	Temperature Conditions for Storage /Shipping
Blood  (Section 14.4)	Mandatory	Whole Blood	Red top	10 mL	X	X	X	Yes	-80 degrees Centigrade
Urine  (Section 14.4)	Mandatory	24 hour urine		10 mL	X		X	Yes	-80 degrees Centigrade

1. Blood draw timed with dropping off of the 24 hour urine collection.

2. The patient may pick up kit prior to starting the infusion but must wait to start collection until infusion has been completed.

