### 14.4 Background and Methodology

14.41 Serum tryptase will be measured with a quantitative enzyme-linked immunosorbent assay [59-61]. Based on previous data from our group, we anticipate a level of 11 ng/mL or greater at time point #1 in patients at risk for a hypersensitivity reaction (we hypothesize we will subsequently observe this reaction in the placebo group, although we will be agnostic to biomarker results at the time of carboplatin infusion) with a drop to below this level with lipids and no change with placebo at time point #2, and with a sustained drop with lipids and no change with placebo at time point #3 [59-61].

14.42 11-beta PGF2a, the most abundant prostaglandin D2 metabolite, will be assessed with a 24 hour urine collection with an immunoassay kit at time points #1 and #3. We anticipate a level of >1000 ng/24 hours or greater in patients about to sustain a carboplatin reaction at time point #1 (we hypothesize we will subsequently observe this reaction in the placebo group, although we will be agnostic to real time biomarker results during the carboplatin infusion) with a drop to below this level with lipids and no change with placebo at time point #3 [59-61].

- 14.43 Leukotriene E4 will be measured in urine with liquid chromatography-tandem mass spectrometry. We anticipate a concentration of >104 pg/mg or greater at time at time point #1 in patients about to sustain a carboplatin reaction (we hypothesize we will subsequently observe this reaction in the placebo group, although we will again be agnostic to real time biomarker results) with a drop with lipids and no change with placebo at time point #3 [59-61].
- 14.44 N-methylhistamine will be also assessed in urine. We anticipate a level of >200 mcg/g or greater at time point #1 in patients about to sustain a carboplatin reaction (we hypothesize we will subsequently observe this reaction in the placebo group, although we will again be agnostic to biomarker results) with a drop with lipids and no change with placebo at time point #3 [59-61].

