## 18.3 CRF completion

This study will use Medidata Rave for remote data capture (rdc) of all study data.

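### Exclusion 3.23 on aspirin, NSAIDs and zileuton looks back from registration, but the 11-beta PGF2a urine is collected around an infusion up to 14 days later, with no restriction or check in between

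*Combined protocol and SAP*

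**What the plan says.** **The exclusion.** Section 3.23 excludes patients "Taking aspirin, nonsteroidal anti-inflammatory agents, or zileuton" within the 7 days before registration. The Study Chair may waive it, and the waiver must be documented. No reason is given for the criterion.

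**Start of treatment.** Section 6.5 says "Treatment cannot begin prior to registration and must begin" no more than 14 days after registration. Section 3.13 allows the qualifying infusion up to 30 days after registration, but 6.5 is the tighter limit, so 14 days is used here.

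**Sampling.** The study calendar (4.1) places the research blood and urine "With the first on-study infusion of carboplatin or oxaliplatin". Section 1.9 puts time point #1 in the 24 hours before the lipid or placebo infusion and time point #3 after the platinum infusion. Section 14.42 states that "11-beta PGF2a, the most abundant prostaglandin D2 metabolite, will be assessed with a 24 hour urine collection", at time points #1 and #3. For the collection after infusion, footnote 2 of 14.1 says the patient "must wait to start collection until infusion has been completed".

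**Drugs in between.** The note to 3.14 leaves ancillary treatment to the treating provider. Section 9.1 says "Patients should otherwise receive full and appropriate supportive care as clinically indicated". Neither names aspirin, NSAIDs or zileuton. The calendar schedules a history before registration, reduces the later visits to weight, and has no medication line at sampling.

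**Use of the samples.** Goal 2.2 and section 16.32 ask, in an exploratory way, whether the mediators appear to predict reactions.

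**The concern.** The criterion is tied to one date and the samples to another. If 3.23 exists so that the mediator measurements are taken free of these drugs, its window should end at the sample. It ends at registration, which can be about two weeks earlier.

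The comparison left open is the time point #1 level of 11-beta PGF2a in patients who later react against those who do not. Section 14.42 names a level that it expects in patients about to react, so this is a comparison the plan means to look at. It is not randomised, so the allocation does not protect it. Unrecorded drug use in the week before the urine could blur it, and dates not collected at the time may be hard to recover. Section 1.9 presents this aim as possible groundwork for a larger trial.

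**Working it through.** The plan gives no figure on this point to reproduce. The check is day arithmetic.

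**Inputs**
- Registration is day 0, and the infusion is on day *t*, with *t* at most 14 (6.5).
- Days restricted by 3.23 run from −7 to *L*, where *L* = −1 if registration day is not counted and *L* = 0 if it is. The text does not settle this.
- Time point #1 is on day *u*, where *u* = *t* − 1 or *u* = *t*, since 1.9 says within 24 hours before the lipid or placebo infusion.
- The look-back before the sample is 7 days. This is an assumption, borrowed from 3.23.

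**Formula.** The look-back covers days *u* − 7 to *u* − 1. For *t* of 1 or more, the number of those days inside the 3.23 window is

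coverage = max(0, min(7, *L* + 8 − *u*)).

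**Time point #1**

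| Registration day restricted? | Day of time point #1 | Coverage (days of 7; 0 if negative) | First infusion day with 0 | Start days 1–14 with 0 |
|---|---|---|---|---|
| No | *t* − 1 | 8 − *t* | 8 | 7 of 14 |
| No | *t* | 7 − *t* | 7 | 8 of 14 |
| Yes | *t* − 1 | min(7, 9 − *t*) | 9 | 6 of 14 |
| Yes | *t* | 8 − *t* | 8 | 7 of 14 |

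For example, take an infusion on day 10 with the sample the day before and registration day counted. Then *u* = 9 and the look-back is days 2 to 8. The restricted days end at day 0, so the overlap is 0.

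Under every count, coverage is 0 from infusion day 9 to day 14. Section 6.5 does not bar a same-day start, but allowing day 0 does not change the first day with zero coverage.

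**Time point #3.** With the sample on day *t* + 1, coverage is max(0, min(7, *L* + 7 − *t*)). It reaches 0 at infusion day 6 (*L* = −1) or day 7 (*L* = 0).

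**Latest permitted start.** For an infusion on day 14, the baseline urine starts on about day 13 and the post-infusion urine ends on about day 15. A window from 7 days before the start of the first collection to the end of the last would run from about day 14 − 8 = 6 to day 14 + 1 = 15. The 3.23 window covers none of those days.

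**What the arithmetic does not show.** An uncovered day is not an exposed day. The documents give no rate of use of these drugs and no distribution of start days. The counts above are of possible start days, not of patients.

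**The case against.** **The purpose of 3.23 is not stated.** Its wording also fits a simple screen for use at entry, in which case nothing is mis-timed. Unlike 3.15, it does not mention the specimens. This stands, and the point is conditional on it.

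**Support for an assay purpose is modest.** Section 14.42 describes 11-beta PGF2a as a metabolite of prostaglandin D2. Two titles in the reference list connect this marker with aspirin, one in aspirin-intolerant asthma and one after aspirin challenge. Both titles present it as a sign of mast cell activation. Neither says that ordinary aspirin or NSAID use distorts the measurement. This stands too.

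**Use may already be recorded.** Section 18.3 says "This study will use Medidata Rave for remote data capture (rdc) of all study data", and the forms are not among the documents. A calendar without a medication line does not show that use goes uncaptured. The fix is therefore conditional.

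**The aim is descriptive.** Section 1.9 gives it no sample size calculation, and 16.32 treats any testing as hypothesis-generating. This limits the weight of the point but does not remove the timing gap.

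**Stronger readings that the documents do not support**
- A reader might infer that the mediator results will be biased. No section gives a rate of use, an effect on the assay, or a relation between use and reactions.
- A reader might infer that the lipid-versus-placebo contrast is confounded. Randomisation balances use between arms in expectation, though not reliably with 20 per arm.
- A reader might extend the point to zileuton or to the other three mediators. No section links zileuton to 11-beta PGF2a, and none states how any of these drugs acts on the other assays.
- A reader might infer that waivers hide exposed patients. Waivers must be documented, so those patients can be identified.

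**Conclusion.** The timing gap is real. Section 3.23 ends at registration, the urine may be collected about two weeks later, and no section restricts or schedules a check of these drugs in between. From infusion day 9 (day 7 or 8 under some counts), a patient can satisfy 3.23 and still have used them throughout the week before the baseline urine. If 3.23 is meant to protect the assays, it does not reliably do so.

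This rests on two assumptions: that protecting the assays is the purpose of 3.23, and that 7 days is the relevant look-back. The timing itself is read directly from the protocol.

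The consequence is small. The primary endpoint does not use the assays, and the sample size is unaffected. Only the exploratory mediator aim (2.2, 16.32) is touched, chiefly the comparison of later reactors with non-reactors on 11-beta PGF2a. This is an inexpensive improvement and not a condition for running the trial.

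**What to change.** Keep 3.23 unchanged for eligibility. Unless the case report form already captures it:

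1. Repeat the 3.23 question at time point #1 for the previous 7 days, and continue it through the end of the time point #3 collection, with dates of use.
2. Flag samples with aspirin or NSAID exposure in that period, including those from patients enrolled under a waiver whose dates apply. Zileuton can be recorded because 3.23 names it, but it should not define exposure in the 11-beta PGF2a summary.
3. Summarise 11-beta PGF2a with and without the flagged samples.

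The cost is one dated form item and one descriptive table. The table will have small cells: at most 40 patients, and fewer at time point #3, where 1.9 expects a high likelihood of drop-out. No procedure is added and eligibility does not change. Whether to tie the restriction itself to the first urine collection is a separate choice for the sponsor, because that would limit supportive medication after registration.
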